### **6.3. Exploratory Objective Analyses**

#### **6.3.1. Correlation between Pediatric Pain Questionnaire and Brief Pain Inventory**

The correlation between PPQ and BPI for each item (average pain rating, pain right now rating, worst pain rating) will be assessed. The correlation for all records where both PPQ and BPI data are non-missing at visits across the entire study for all ITT will be assessed by using Pearson's correlation coefficient.

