### **4.3. Exploratory Objectives**

Exploratory objectives of the study are as follows:

- To evaluate the correlation between BPI pain severity items and PPQ pain items.
- To evaluate the appropriateness of the ACR FM criteria (Wolfe et al. 1990) in an adolescent population.

[figure not shown]

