## **5.2. Determination of Sample Size**

Approximately 184 patients will be randomized in a 1:1 ratio to the duloxetine and placebo treatment groups. This study is to assess the difference of the mean change in BPI average pain severity from baseline to the last time point (Visit 8, Week 13) in Study Period II between treatment groups. Assuming that there will be some missing post-baseline data, and about 81% completion rate at acute phase by Visit 8 or Week 13, this sample size will provide at least 80% power to detect the treatment difference of 1.0 point with  $\alpha=.05$ . All the parameters used in the sample size calculations were based on the MMRM analysis of data from 3-month, placebo-controlled, acute treatment period in 2 adult FM studies: Study F1J-MC-HMCA and Study F1J-MC-HMCJ.

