#### 6.1.1. Analysis Populations

All data presentations will be based the intent-to-treat (ITT) population, which includes all randomized patients.

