C-SSRS categorical analyses	All randomized patients entering extension phase.	Lifetime baseline: All Visits 1-8 Lead-in baseline: $7 \leq \text{Visit} \leq 8$	All Visits 8.01-15
Treatment Emergent Abnormal Labs	Patients with normal laboratory values at all nonmissing baseline visits (with respect to direction being analyzed) and who have at least one post-baseline observation	All Visits 2.01-8	All Visits 8.01-15
Treatment emergent low blood pressure	Patients with normal values at all nonmissing baseline visits (with respect to direction being analyzed) and who have at least one post-baseline observation. See Table HMGW.6.4 for normal limits of blood pressure.	Minimum value from Visits 2.01-8	All Visits 8.01-15
PCS in vital signs, weight, sustained blood pressure analyses	Vital signs: Patients with normal values at all nonmissing baseline visits (with respect to direction being analyzed) and who have at least one post-baseline observation. See Table HMGW.6.4 for normal limits of vital signs. Weight: Patients with non-missing baseline and at least one post-baseline value.	Low: Minimum value from Visits 2.01-8 High: Maximum value from Visits 2.01-8	All Visits 8.01-15
Treatment-emergent changes in ECG intervals and heart rate	Patients with normal values at all nonmissing baseline visits (with	Low: Minimum value	All Visits 8.01-15

	respect to direction being analyzed) and who have at least one post-baseline observation. See Table HMGW.6.8 for normal limits of ECG.	from Visits 2.01–8 High: Maximum value from Visits 2.01–8	
Continuous Safety measures	Patients with a baseline and at least one post-baseline observation	Last of Visits 3-8 (for vital sign analysis, another baseline is: Last of Visits 1-2)	All Visits 9-15
Acute and Extension Phase Combined			
Efficacy	Patients with a baseline and at least one post-baseline observation	Last of Visits 1-2	All Visits 3-15
Treatment emergent low blood pressure	Patients with normal values at all nonmissing baseline visits (with respect to direction being analyzed) and who have at least one post-baseline observation. See Table HMGW.6.4 for normal limits of blood pressure.	Minimum value from Visits 1-2	All Visits 2.01-15

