A repeated measures analysis refers to a restricted maximum likelihood (REML)-based, mixed-effects repeated measures (MMRM) analysis using all the longitudinal observations at each post-baseline visit. The model for this analysis will include the fixed categorical effect of treatment, pooled investigative site, visit, and treatment-by-visit interaction, as well as the continuous, fixed covariate of baseline value of the variable being analyzed and baseline value of the variable being analyzed-by-visit interaction. An unstructured covariance structure will be used to model the within-patient errors. And Kenward-Roger approximation (Kenward and Roger, 1997) will be used to estimate denominator degrees of freedom. If the default Newton-Raphson algorithm used by SAS PROC MIXED does not converge, then the Fisher scoring algorithm will be applied.

However, if the model with unstructured covariance structure still fails to converge, the sandwich estimator (Diggle, Liang, and Zeger, 1994; Lu and Mehrotra, 2009) will be used to estimate the standard errors of the fixed effects parameters and the model will be fitted using covariance structures in the following order until convergence is met:

heterogeneous toeplitz	type = toeph
heterogeneous autoregressive (1st order)	type = arh(1)
heterogeneous compound symmetric	type = cs(h)
toeplitz	type = toep
autoregressive (1st order)	type = ar(1)
compound symmetric	type = cs

When the sandwich estimator is used, the Kenward-Roger approximation for denominator degrees of freedom cannot be used. Instead, the denominator degrees of freedom will be partitioned into between-subject and within-subject portions (denoted by DDFM= BETWITHIN in the MODEL statement).

For repeated measures analyses of efficacy and safety variables that are not collected at each post-baseline visit, data may exist at visits where the variable was not scheduled to be collected due to early discontinuation visits. Data collected at scheduled visits and early discontinuation visits will be used in the analysis. In these situations, the data from the early discontinuation visit will be carried forward to the next regularly scheduled collection visit for the repeated measures analysis. Significance tests will be based on least-squares means (LSMean) and Type III sum-of-squares, using a two-sided  $\alpha=0.05$ . Analyses will be implemented using SAS® PROC MIXED.

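### The PPQ–BPI correlations pool all patient-visit records, so each coefficient mixes between-patient, within-patient and time-trend correlation and is hard to interpret

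*SAP*

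**What the plan says.** SAP Section 4.3 lists as an exploratory objective: "To evaluate the correlation between BPI pain severity items and PPQ pain items". Section 6.3.1 holds the only analysis for it. The items are fixed first: "The correlation between PPQ and BPI for each item (average pain rating, pain right now rating, worst pain rating) will be assessed". The records to be used come next: "The correlation for all records where both PPQ and BPI data are non-missing at visits across the entire study". The population and the statistic are then named: "for all ITT will be assessed by using Pearson's correlation coefficient". The ITT set is defined in Section 6.1.1 as the "intent-to-treat (ITT) population, which includes all randomized patients".

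The unit is therefore the patient-visit record, with both arms and all study periods pooled, and there are three coefficients, one per item. Section 6.3.1 gives no coefficient at baseline or by visit, no correlation of changes, no split into between- and within-patient parts, and no allowance for repeated records. It also plans no confidence interval, test or threshold.

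Elsewhere the SAP does allow for repeated records. For the repeated measures analyses, Section 6.1.2 states: "An unstructured covariance structure will be used to model the within-patient errors".

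**The concern.** A correlation between two pain scales can answer two useful questions: whether patients who score high on one also score high on the other at a given time, and whether a patient whose score changes on one changes likewise on the other. Pooling all visits blends the two and adds a third source, a mean fall in pain on both scales, which raises the coefficient even if the scales are only loosely related within patients. Patients who remain into the extension also supply more records than those who leave early.

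The second question matters because the PPQ items are secondary efficacy measures analysed as change from baseline (Table HMGW.6.3, items 2.d and 3.b). A pooled coefficient can suggest that the PPQ tracks BPI change more closely than it does. What is at stake is the reading of one exploratory table.

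**Working it through.** The SAP states no expected correlation, so there is no figure to reproduce. The check asks what a pooled coefficient estimates and how far it can lie from the alternatives.

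**Inputs from the SAP.** About 184 patients randomised 1:1 (Section 5.2). The combined phases run from Visits 1–2 to Visit 15 (Table HMGW.6.1). The PPQ schedule is not given.

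**Assumptions.** Variances equal on the two scales; a linear mean fall of 2 points on both; between-patient correlation 0.8; within-patient correlation 0.2 to 0.4; between- and within-patient variances 2.3 and 1.7; no dropout; *m* equally spaced paired records per patient. The SAP's only mean-change figure is 3 to 4 points among adult responders (Section 6.1.13.2), which does not fix the fall for all patients or for the PPQ.

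**Decomposition.** Let *b*, *t* and *w* be the between-patient, shared-trend and within-patient variances. A shared trend has correlation 1, so

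- same-visit r = (b·r_b + w·r_w) / (b + w)
- pooled r = (b·r_b + t + w·r_w) / (b + t + w)
- correlation of changes = r_w, when within-patient deviations are independent between visits

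A linear fall of 2 points over *m* records gives t = 4(m + 1) / [12(m − 1)].

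**Numbers for m = 14**, where t = 60/156 = 0.385:

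| r_w | same-visit r | pooled r | r of changes |
|---|---|---|---|
| 0.2 | (1.84 + 0.34)/4 = 0.545 | (2.18 + 0.385)/4.385 = 0.585 | 0.20 |
| 0.4 | (1.84 + 0.68)/4 = 0.63 | (2.52 + 0.385)/4.385 = 0.66 | 0.40 |

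Simulation with the same between- and within-patient correlations and a 2-point fall gave same-visit values of 0.54 to 0.63 and pooled values of 0.58 to 0.65, a shift of 0.02 to 0.04. With m = 3, t = 16/24 = 0.667 and the pooled values are 2.847/4.667 = 0.61 and 3.187/4.667 = 0.68, so fewer PPQ visits do not remove the effect.

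**Entry floor.** Table HMGW.6.2 treats a BPI average pain score below 4 at Visit 1 or 2 as an eligibility deviation, so the baseline range of that item is restricted. Simulation with integer 0–10 scores, this floor and 14 records gave baseline r 0.45–0.53, later same-visit r 0.49–0.58, pooled r 0.53–0.62 and correlation of changes 0.19–0.36. The pooled figure exceeds every same-visit figure and is far above the correlation of changes.

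**A more contrasted case.** With b = w = 2, r_b = 0.9 and r_w = 0.3, the pooled r is (1.8 + 0.6)/4 = 0.60 without trend, 2.9/4.5 = 0.64 with t = 0.5, and 3.4/5 = 0.68 with t = 1. It matches neither component.

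**Precision, only if an interval or p-value is printed.** Over 2,000 simulated data sets per setting, with 184 patients, a nominal 95% Fisher-z interval that counts every record as independent covered the pooled target as follows:

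| records per patient | coverage |
|---|---|
| 3 | 84–92% |
| 6 | 73–88% |
| 14 | 53–77% |

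The true standard deviation of r was about 1.1 times (0.0281/0.0249) to 2.7 times (0.0363/0.0136) the naive standard error. The mean simulated r equalled the pooled target to within 0.003.

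**The case against.** The case for leaving the section alone is substantial.

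- **No inference is planned.** A Pearson point estimate does not require independent records; only its standard error does. A reader might infer that the section produces invalid p-values, but it names none. This stands, so the precision point is conditional.
- **The coefficient is not biased for what it estimates.** A reader might call it biased, or a faulty measure of agreement. The simulations show no meaningful bias for the pooled target, and the SAP's objective is correlation, not agreement. The fault is that the target is hard to interpret.
- **The shift from the same-visit value is small.** At 0.02 to 0.04 with 14 records, it would not change the reading of an exploratory correlation. This stands; the larger gap is to the correlation of changes.
- **Fourteen records per patient is unsupported.** Only records with both scales count. The PPQ is absent from the by-visit list (Table HMGW.6.3, item 4), Section 6.1.2 notes that some variables are not collected at every visit, and Section 5.2 assumes about 81% complete the acute phase. This stands, so the coverage figures for 14 records are near a worst case.
- **Pooling widens the score range.** Given the entry floor, a baseline-only coefficient for average pain is likely attenuated. This is a fair reason not to rely on baseline alone, but it does not justify pooling, because post-baseline visits have no such floor and can be reported separately.
- **No decision depends on the result.** This is true, and it sets the importance.

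**Conclusion.** The point holds at low importance. Each of the three coefficients is a mix whose weights depend on the variance components, the size of any shared trend and how long patients stay. It answers neither the across-patient nor the within-patient question. Under the assumed inputs it sits slightly above the same-visit correlation (by 0.02 to 0.04 with 14 records) and well above the correlation of changes (about 0.53–0.62 against 0.19–0.36 in the simulation with the entry floor). All variance components, component correlations and record counts are assumptions, so these figures illustrate direction and rough size only.

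The documents do not support reading this as a planned invalid test, as a biased estimate of a quantity the SAP promised, or as a threat to the primary analysis, the error rate or the sample size.

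**What to change.** In Section 6.3.1, for each of the three items:

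1. Report Pearson's r with one record per patient at baseline and at each visit where both scales are collected. Note that the entry criterion restricts the baseline range of BPI average pain.
2. Add the correlation of changes from baseline to Visit 8, or to the last acute-phase visit with both scales.
3. If an overall figure is kept, take it from a repeated-measures or bivariate mixed model that separates between- and within-patient correlation, with any confidence interval clustered by patient.

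The same data serve throughout. Items 1 and 2 cost a few more rows in an exploratory table; item 3 needs one additional model and only if a single figure is wanted.

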#### **6.3.2. Appropriateness of ACR criteria**

Patients meet the American College of Rheumatology (ACR) criteria for fibromyalgia (Wolfe et al. 1990) if the following criteria are met:

- History of widespread pain  $\geq 3$  months (pain in the left and right side of the body, and pain above and below the waist, and axial skeletal pain)
- Tenderness in 11 or more of 18 specific points on digital palpation

The number and frequency of randomized patients who meet the ACR criteria for fibromyalgia will be summarized. McNemar test will be used to assess the agreement between ACR criteria and JPFS criteria defined by Yunus and Masi (Yunus and Masi, 1985). Also, the baseline

demographic characteristics and baseline illness characteristic will be summarized by treatment group for the patients who meet JPFS criteria but not ACR criteria.

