## 4. Study Objectives

### 4.1. Primary Objective

The primary objective of this study is to evaluate the efficacy of duloxetine 30/60 mg once daily (QD) compared with placebo on the reduction of average pain severity as measured by the Brief Pain Inventory (BPI) – Modified Short Form: Adolescent Version 24-hour average pain severity rating (for simplicity, it is referred to as the BPI average pain severity hereafter) during a 13-week, double-blind treatment phase in adolescents (aged 13 to 17 years) with Juvenile Primary Fibromyalgia Syndrome (JPFS), as defined by Yunus and Masi (Yunus and Masi 1985).

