**Table HMGW.6.2 Definition of Significant Protocol Deviations**

Category of Protocol Deviation	Details	Methods of Checking
Improper administration of ICF	ICF not signed prior to initiation of protocol procedures	For all patients, if ICF (including assent form if applicable) date is after Visit 1 date or Visit 1 lab date, then result is a protocol deviation.
Inclusion/exclusion criteria	Randomized patient <13 years old at study entry	For randomized patient, if age<13 at ICF date, then result is a protocol deviation [criterion 1]
	Randomized patient >=18 years old at study entry	For randomized patient, if age >=18 at Visit 1 date, then result is protocol deviation [criterion 1]
	Randomized patient does not meet criteria for primary JPFS as defined by Yunus and Masi	For randomized patient, if JPFS criteria are not met at Visit 1, then result is protocol deviation. [criterion 2]
	Randomized patient does not have a score of ≥4 on BPI average pain severity at Visit 1 and Visit 2	For randomized patient, if BPI item #3 <4 at Visit 1 or Visit 2, then result is protocol deviation. [criterion 3]
	Randomized female patient tested positive for pregnancy	For randomized female patients, if pregnancy test is positive any time prior to Visit 2, then result is protocol deviation.

	[criterion 4]
Randomized patient had current diagnosis of <XXX> at study entry	For randomized patients, use Pre-existing conditions and study adverse event module. If there exists a current diagnosis of rheumatoid arthritis, arthritis, lupus, ankylosing spondylitis, psoriasis, then result is protocol deviation. [criterion 17]
Randomized patient had current diagnosis or diagnosis within 1 year of <XXX> at study entry	For randomized patients, use Pre-existing conditions and study adverse event module. If there exists a current diagnosis or diagnosis within 365 days (1 year) prior to visit 1 of bipolar disorder, psychotic depression, schizophrenia or other psychotic disorder, anorexia, bulimia, obsessive compulsive disorder, posttraumatic stress disorder, panic disorder, pervasive development disorder, then result is protocol deviation. [criterion 18]

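### The McNemar test of ACR against JPFS criteria is run in patients selected for meeting JPFS, so its p-value reflects little beyond the ACR-negative count and does not measure agreement

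*SAP*

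**What the plan says.** One exploratory objective in SAP section 4.3 is to judge whether the ACR fibromyalgia criteria are appropriate in adolescents. Section 6.3.2 gives three analyses for it:

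- A count: "The number and frequency of randomized patients who meet the ACR criteria for fibromyalgia will be summarized".
- A test: "McNemar test will be used to assess the agreement between ACR criteria and JPFS criteria".
- A description of baseline demographic and illness characteristics, "summarized by treatment group for the patients who meet JPFS criteria but not ACR criteria".

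The sentence on the test names no analysis set and no version of the test (exact, uncorrected or continuity-corrected). Section 6.1.1 bases all data presentations on the ITT population, "which includes all randomized patients". Section 6.1.2 sets a two-sided 0.05 level unless otherwise specified.

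Table HMGW.6.2 in section 6.1.9 lists the JPFS requirement as criterion 2 among the inclusion and exclusion criteria: "For randomized patient, if JPFS criteria are not met at Visit 1, then result is protocol deviation". The primary objective in section 4.1 likewise defines the trial population by the JPFS criteria.

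**The concern.** A comparison of two sets of diagnostic criteria needs patients who could be positive or negative on either one. Here every correctly enrolled patient is JPFS-positive, so the 2×2 table has one filled row. The McNemar null hypothesis, equal positive rates under the two criteria, then says that every enrolled patient meets ACR. A single ACR-negative patient disproves it without any test.

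The second problem does not depend on who is analysed. McNemar's test asks whether the discordant patients split evenly between the two directions. It does not ask how many patients are discordant, which is what agreement means.

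At stake is the reading of the only inferential step planned for this objective. A significant p-value reported as a result on agreement could be taken to show that ACR is unsuitable in adolescents when nearly all patients meet both sets of criteria.

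**Working it through.** The SAP gives no figure for this analysis, so there is none to reproduce.

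**Inputs**

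- N = 184, the planned number randomized (section 5.2).
- Two-sided level 0.05 (section 6.1.2).
- k = patients who are JPFS-positive and ACR-negative. Not stated; assumed over a range.
- c = patients who are JPFS-negative and ACR-positive. Zero by design; 1 to 3 assumed for entry deviators.

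**Formulas**

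- Exact: two-sided binomial test with probability 0.5 on k + c discordant patients. With c = 0 this is p = 2 × 0.5^k.
- Uncorrected: χ² = (k − c)²/(k + c) on 1 df, which equals k when c = 0.
- Continuity-corrected: χ² = (|k − c| − 1)²/(k + c) on 1 df.

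**No deviators (c = 0)**

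| k | Meet both criteria | Exact p | Uncorrected p | Corrected p |
|---|---|---|---|---|
| 4 | 180/184 = 97.8% | 0.125 | 0.0455 | 0.134 |
| 5 | 179/184 = 97.3% | 0.0625 | 0.025 | 0.074 |
| 6 | 178/184 = 96.7% | 0.031 | 0.014 | 0.041 |
| 9 | 175/184 = 95.1% | 0.0039 | 0.0027 | 0.0077 |

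N enters none of the three formulas; it is used only to express k as a percentage. The uncorrected test is significant from k = 4, the exact and corrected versions from k = 6. At k = 4 or 5 the verdict therefore rests on a choice the SAP does not make.

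**With ACR-positive, JPFS-negative deviators (exact p)**

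| k | c = 0 | c = 1 | c = 3 |
|---|---|---|---|
| 6 | 0.031 | 0.125 | 0.51 |
| 9 | 0.0039 | 0.0215 | 0.146 |

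For example, k = 6 and c = 1 gives 2 × (7 + 1)/2⁷ = 16/128 = 0.125. The smallest k for exact significance is 6, 8, 10 and 12 for c = 0, 1, 2 and 3.

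**The test does not follow agreement.** Take a general table of 184 patients, not one this design could produce, with 20 discordant patients in each direction. Then 40/184 = 21.7% are classified differently, yet p = 1.0.

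**Kappa would not help.** If all patients are JPFS-positive, observed agreement is (184 − k)/184. Chance-expected agreement is 1 × (184 − k)/184, the same number. Kappa is therefore 0 for any k from 1 upwards.

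**What the sample can support.** The share of JPFS-positive patients who meet ACR can be estimated. With k = 9 it is 175/184 = 95.1%, exact 95% CI 90.9% to 97.7%. With k = 6 it is 178/184 = 96.7%, exact 95% CI 93.0% to 98.8%.

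**The case against.** **The population is inferred.** The sentence on the test names none, and JPFS is checked at Visit 1, before randomization. If screen failures with both assessments were included, the JPFS-negative row would not be empty. Whether such data exist depends on the protocol, which was not available. The sentence before it and section 6.1.1 both point to randomized patients, so the reading holds, with some uncertainty. The argument that McNemar compares margins does not depend on it.

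**The fragility is confined to small k.** With k = 9 one deviator leaves the exact test significant (p = 0.0215), and with k = 20 and three deviators p is about 0.0005. Nothing in the SAP says where k will fall. A deviator also matters only if ACR-positive, since one who meets neither set of criteria is concordant. This is right, and the claim is limited accordingly. At larger k the result is stable but still not a measure of agreement.

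**Equal margins are one component of agreement, so relabelling might suffice.** Calling the test a comparison of classification rates would mend the wording. It would not mend the selection, because one of the two rates is fixed at 100% by the entry criterion.

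**The practical harm is small.** The objective is exploratory, section 6.3.2 attaches no decision rule to it, and the planned ACR frequency would stand beside the p-value. This stands in full and sets the severity.

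**Conclusion.** The concern holds, as a minor point. As written, section 6.3.2 applies a test that does not measure agreement, in patients selected on one of the two sets of criteria being compared. Without deviators the p-value depends only on k; a few ACR-positive deviators move the cut-off without changing that conclusion. Significance can arise when about 97% of patients meet both criteria: from 4 ACR-negative patients of 184 with the uncorrected test, or 6 with the exact test.

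This rests on reading the analysis set as randomized patients and on assumed values of k and c. The primary analysis is untouched. The planned ACR frequency and the description of JPFS-positive, ACR-negative patients remain valid and partly serve the objective.

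**What to change.** In section 6.3.2, delete the sentence on the McNemar test. In its place, report the number and proportion of randomized patients meeting ACR among those who met the JPFS criteria at Visit 1, with an exact (Clopper-Pearson) 95% confidence interval. This narrows the denominator slightly from all randomized patients, and the two coincide if there are no entry deviators. State that agreement between the two sets of criteria is not assessed in randomized patients. Keep the rest of the section.

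The cost is one SAP sentence and a trivial program change. It needs no new data, and one exploratory p-value is lost.
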